If the final data indicates any difference in the rate of knee replacement between the CMT and control arm (see section on Economic Analysis), we will seek further funding to follow participants for a 10-year period. By accessing the HES (Hospital Episode Statistics) database along with the National Joint Registry (NJR), we will obtain data on the numbers of participants in each arm who opt for surgery each year for a period of 10 years after the trial. These data will be combined with data collected during this study. We have communicated our intent to HES and NRJ who are supportive of our plans. Following their advice, we have explicitly stated in the consent materials that NHS number and date of birth will be sent to HES/NRJ so that we can access health information.

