### Follow-up:

Following treatment, participants in the CMT arm will be sent an information letter/email explaining next steps of the trial (see 'Group 1 follow up information letter'). Participants in the control arm will also be sent an information letter (see 'Group 2 follow up information letter'). These letters/emails will inform participants of the dates that the follow-up questionnaire will be sent out.

At the two follow-up points, participants will receive a letter/email inviting them to complete outcome data (see 'Six-month questionnaire cover letter' and 'Twelve-month questionnaire cover letter'). For participants who opt to complete outcomes electronically, this letter will be sent via REDCap and contain a link to the online survey to complete outcomes. For those who opt for paper-based outcomes, this letter will be posted with the booklet of questionnaires.

A member of the research team who is blinded to treatment allocation will monitor return of all outcome data. This monitoring will allow the research team to identify missing outcome data and send reminders as appropriate. Reminders for the 6-month and 12-month outcome data will follow the schedule below:

- **At 3 days after the initial invitation to complete outcomes is sent**, if outcome data not completed, a Trial Administrator (or the REDCap system) will e-mail the participant with a reminder to complete outcomes (see 'Six-month questionnaire reminder letter' and 'Twelve-month questionnaire reminder letter').
- **At 1 week after the initial invitation to complete outcomes is sent**, if outcome data not completed, a Trial Administrator (or the REDCap system) will e-mail the participant again with a reminder to complete outcomes.
- **At 2 weeks after the initial invitation to complete outcomes is sent**, if outcome data not completed, a Trial Administrator (or the REDCap system) will e-mail the participant again with a reminder to complete outcomes. A text message will also be sent to the participant, and they will receive a follow-up call from a trial administrator.
- **At 3 weeks after the initial invitation to complete outcomes is sent**, if outcome data not completed, a trial administrator (blinded to group allocation), will telephone the participant to obtain a minimal data set. This minimal dataset will include the WOMAC questionnaire, the GAKS, and the EQ-5D-5L.

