### 10.4 Primary outcome analysis

*Population:* All participants

*Treatments:* CMT + Usual care vs usual care alone , regardless of non-adherence or receipt of surgery to treat knee OA.

*Primary outcome:* Mean difference in WOMAC composite score at 12-month follow-up

*Handling of intercurrent events*

- Failure to complete CMT (attending fewer than 6 out of 7 sessions) – Treatment policy strategy
- Surgery to treat knee OA – Treatment policy strategy

The primary analysis will adopt a treatment policy strategy in line with the ICH E9(R1) estimand framework. All intercurrent events occurring after randomisation, including failure to complete the CMT intervention

(attending fewer than 6 out of 7 sessions) or undergoing knee surgery, will be considered part of the treatment effect. Participants will be analysed in the arm to which they were randomised regardless of these events. The primary outcome will be the adjusted mean difference in WOMAC composite score at 12 months: this will be estimated using a linear multilevel analysis of covariance (ANCOVA) model, including treatment arm (fixed effect), baseline WOMAC as a covariate, and site and receipt of surgery as random effects. The estimate of the difference for the WOMAC composite score between intervention arms will be presented with 95% confidence intervals and p-values: statistical tests will be two-sided. Missing primary outcome data will be replaced using multiple imputation under missing-at-random assumptions, and analyses will be conducted using the Stata MI command.

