## 10.5 Secondary outcome analysis

Secondary outcomes, including those measured at 6-month follow-up, will be analysed using methodology consistent with the primary outcome analysis. All participants will be analysed in the arm to which they were randomised, regardless of adherence to the CMT intervention or receipt of knee surgery, in line with a treatment policy strategy.

The following secondary outcomes will be analysed:

- Composite WOMAC score at 6 months post-randomisation
- WOMAC subscales (pain, function, stiffness) at 6 and 12 months
- Pain Catastrophizing Scale (PCS) at 6 and 12 months
- Pain Self-Efficacy Questionnaire (PSEQ) at 6 and 12 months
- Work Productivity and Activity Impairment Questionnaire (WPAI-OA) at 6 and 12 months
- Health-related quality of life using the EQ-5D-5L at 6 and 12 months

Descriptive statistics will be provided for the Global assessment of knee symptoms (GAKS) at 6 and 12 months to understand differences between the intervention and control.

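### The primary model conditions on knee surgery after randomisation, so it does not estimate the treatment-policy effect that section 10.4 declares

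*Protocol*

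**What the plan says.** Protocol section 10.4 states the estimand and the model together.

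- The arms are compared "regardless of non-adherence or receipt of surgery to treat knee OA".
- The list of intercurrent events has the entry "Surgery to treat knee OA – Treatment policy strategy".
- Events after randomisation, such as missing CMT sessions "or undergoing knee surgery, will be considered part of the treatment effect".
- The primary estimate is an adjusted mean difference in 12-month composite WOMAC from a multilevel ANCOVA. Arm is a fixed effect, with "baseline WOMAC as a covariate, and site and receipt of surgery as random effects".

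Section 10.5 says that secondary outcomes "will be analysed using methodology consistent with the primary outcome analysis", and that participants are analysed "regardless of adherence to the CMT intervention or receipt of knee surgery, in line with a treatment policy strategy".

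Section 8.7 plans longer follow-up under a condition: "If the final data indicates any difference in the rate of knee replacement between the CMT and control arm". Section 10.9 plans a lifetime-horizon analysis under a similar condition.

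**The concern.** Receipt of surgery is observed after randomisation and can itself depend on the arm. Usual care includes surgery (section 6.1), CMT is placed before orthopaedic referral (section 2), and the protocol allows that knee-replacement rates may differ. Surgery can also change the 12-month WOMAC.

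Putting it in the outcome model does two things. It removes the part of the arm difference that runs through surgery, which section 10.4 says belongs to the treatment effect. It also makes the comparison depend on who is selected for surgery in each arm, so randomisation no longer protects it.

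At stake is what the headline result means. The report would describe a treatment-policy effect while the model estimates something else, and the same would hold for the secondary outcomes.

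**Working it through.** **The plan's own figures.** Section 10.1 gives a baseline mean (SD) of 41.3 (17.8). The target is 0.20 × 41.3 = 8.26, stated as 8.3, and 8.26 / 17.8 = 0.464, stated as 0.46. For d = 0.46, two-sided 5% and 90% power, the normal approximation gives 100 per group. The t-based calculation gives 101 (power 0.902), as stated. Attrition of 20% gives 101 / 0.8 = 126.25, stated as 126. The surgery term plays no part in this calculation.

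**Can the text be read consistently?** Receipt of surgery repeats the intercurrent-event wording of the same section, so it does not mean surgery before baseline. Section 10.6 offers a per-protocol and a complete-case analysis. The first restricts the population and the second changes only the handling of missing data. Neither gives a full-population estimate without the surgery term.

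**Size in principle.** Let δ be the direct CMT effect, s the effect of surgery on WOMAC, and pC and pT the surgery rates in control and CMT.

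- Treatment-policy effect = δ + s(pT − pC).
- With no selection into surgery, a model that conditions on surgery estimates δ.
- Distortion = δ − [δ + s(pT − pC)] = s(pC − pT).

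Example: pC = 0.15, pT = 0.05, s = −15 gives −15 × 0.10 = −1.5 points. With s = +15 it is +1.5.

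**Simulation.** From the protocol: 101 per arm, 6 sites, baseline 41.3 (17.8), δ = −8.3. Assumed: baseline–outcome correlation 0.5, site SD 2, and all surgery rates and effects. There were 400 runs per row. Selection means that participants with worse scores are likelier to have surgery (latent correlation 0.5). A negative last column favours CMT.

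| Surgery, control / CMT | s | Selection | True effect | Model without surgery | Model as written | As written minus true |
|---|---|---|---|---|---|---|
| 10% / 10% | −15 | none | −8.30 | −8.27 | −8.28 | +0.02 |
| 5% / 2% | −15 | none | −7.85 | −7.88 | −8.25 | −0.40 |
| 15% / 5% | −15 | none | −6.80 | −6.70 | −8.06 | −1.26 |
| 15% / 5% | −25 | none | −5.80 | −5.71 | −8.11 | −2.31 |
| 20% / 5% | −20 | none | −5.30 | −5.25 | −8.18 | −2.88 |
| 15% / 5% | +15 | none | −9.80 | −9.65 | −8.28 | +1.52 |
| 15% / 5%, δ = 0 | −25 | none | +2.50 | +2.58 | +0.14 | −2.36 |
| 15% / 5% | −15 | 0.5 | −6.80 | −6.80 | −6.90 | −0.10 |
| 15% / 5% | 0 | 0.5 | −8.30 | −8.56 | −7.36 | +0.94 |

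The simulation error of each mean is about 0.11: residual SD 17.8 × √(1 − 0.25) = 15.4, standard error 15.4 × √(2/101) = 2.17, and 2.17 / √400 = 0.11. The model without surgery tracks the true effect, with a largest gap of 0.26 in the last row. Measured against that model instead of the true value, the last-row shift is −7.36 − (−8.56) = +1.20.

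**Does random help?** In every row the random-effect fit lies within about 0.15 points of a fit with surgery as a fixed covariate, so on average the conditioning is the same. The variance has only two levels behind it, however. In a further simulation (120 runs; surgery 10% vs 5%, s = −10, severity driving both surgery and outcome), it was estimated as about zero in 61% of runs. The term then drops out. Bias was negligible there (−7.93 without the term, −7.94 with it), but whether any adjustment happens would be settled by chance.

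**The case against.** The best defence is that the intent is plain: section 10.4 says three times that surgery does not change the comparison, and the bias may be small. The second part stands as far as it goes. With equal rates there was no distortion, with 5% vs 2% it was about 0.4 points, and with selection at s = −15 it was about 0.1. But the protocol names every model term, so this is not a detail left open for a statistical analysis plan, and nothing else in it removes the term.

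A reader might infer four stronger points that the document does not support.

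- **That the protocol expects CMT to reduce knee replacement.** Sections 8.7 and 10.9 are conditional, and neither gives a direction. Section 6.2 cites a link between muscle overactivity and later replacement at five years, which is no forecast for 12 months.
- **That the error flatters CMT.** It does when control participants have more surgery and benefit from it. A harmful effect of surgery at 12 months, or selection of worse patients, pushes the other way (+1.52 and +0.94 above).
- **That a yes/no factor cannot be a random effect.** Its variance can be estimated by REML, but very imprecisely.
- **That surgery status comes only from the healthcare-use questionnaire.** That is the main source, but section 9.2.1 puts a serious-adverse-event question to both arms at six months. The route is partial: section 9.1.2 exempts elective or pre-planned treatment for a pre-existing condition, and the recording period ends at six months.

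**Conclusion.** Wrong as written. The model in section 10.4 does not estimate the treatment-policy effect that the section declares, and section 10.5 passes the inconsistency to the secondary outcomes. This conclusion needs no assumption about rates; it follows from setting the estimand beside the model terms.

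The size does rest on assumptions, because the protocol gives no surgery rates, surgery effects or selection strength. Across the scenarios shown it runs from nil to 2.88 points, or 2.88 / 8.3 = 35% of the target difference. The largest shift against CMT was 1.52 points (18%). Because s(pC − pT) changes sign with either factor, the direction cannot be known in advance.

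**What to change.** In section 10.4, delete receipt of surgery from the model and keep arm, baseline WOMAC and site. In section 10.5, apply the same to the secondary outcomes, each with its own baseline score where one exists. Report surgery by arm descriptively. If an effect that accounts for surgery is wanted, define it as a separate supplementary estimand with its own strategy and analysis.

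The text change is one phrase, made through the amendment process of section 13.5, with no extra participants. With equal surgery rates, simulated power was 0.94 without the term and 0.96 with it. Where surgery narrows the gap between arms, power falls further (0.83 against 0.94 at 15% vs 5%, s = −15). That is because the declared effect is then smaller than 8.3, and a model that hides this is not a remedy.

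Separate and minor: section 8.8 says of the telephone fallback, "This minimal dataset will include the WOMAC questionnaire, the GAKS, and the EQ-5D-5L". It omits the healthcare-use questionnaire, so telephone responders may have a WOMAC score but unknown surgery status. Once the term is deleted the primary model no longer needs that status. The per-protocol set of section 10.6 and the knee-replacement comparison still do, and one question on knee surgery since randomisation would cover both.

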## 10.5 Secondary outcome analysis

Secondary outcomes, including those measured at 6-month follow-up, will be analysed using methodology consistent with the primary outcome analysis. All participants will be analysed in the arm to which they were randomised, regardless of adherence to the CMT intervention or receipt of knee surgery, in line with a treatment policy strategy.

The following secondary outcomes will be analysed:

- Composite WOMAC score at 6 months post-randomisation
- WOMAC subscales (pain, function, stiffness) at 6 and 12 months
- Pain Catastrophizing Scale (PCS) at 6 and 12 months
- Pain Self-Efficacy Questionnaire (PSEQ) at 6 and 12 months
- Work Productivity and Activity Impairment Questionnaire (WPAI-OA) at 6 and 12 months
- Health-related quality of life using the EQ-5D-5L at 6 and 12 months

Descriptive statistics will be provided for the Global assessment of knee symptoms (GAKS) at 6 and 12 months to understand differences between the intervention and control.

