## 3 OBJECTIVES AND OUTCOME MEASURES/ENDPOINTS

### 3.1 Aims

The primary aim is to assess whether Cognitive Muscular Therapy (CMT) + usual care results in less knee pain and disability at 1-year post-randomisation compared to usual care alone. We hypothesise that CMT + usual care will be associated with lower composite WOMAC scores at 1 year in comparison to usual care alone for people with a clinical diagnosis of knee OA (OA), who are dissatisfied with the outcome of therapeutic exercise.

Secondary aims include:

- Estimates of treatment effects across a range of secondary outcomes including knee pain, knee function, knee stiffness, pain catastrophizing, pain self-efficacy, global assessment of knee symptoms, quality of life, the impact of knee OA on capacity to work, healthcare use (including knee replacement surgery) and adverse events up to 12-months.
- Within-trial cost utility analysis from an NHS and PSS perspective.
- Qualitative exploration of participants and physiotherapists' experiences and perception of the CMT intervention, beliefs around implementation and involvement in the trial.

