### 3.3 Secondary Outcome measures and endpoints

- Composite WOMAC score [19] at 6-months post-randomisation
- WOMAC pain subscale [19] at 6- and 12-months post-randomisation
- WOMAC function subscale [19] at 6- and 12-months post-randomisation
- WOMAC stiffness subscale [19] at 6- and 12-months post-randomisation
- Global assessment of knee symptoms (GAKS) at 6- and 12-months post-randomisation [24]

- Pain catastrophizing scale (PCS) [25] at 6- and 12-months post-randomisation
- Pain self-efficacy questionnaire (PSEQ) [26] at 6- and 12-months post-randomisation
- Impact of knee OA on capacity to work will be measured with the Work Productivity and Activity Impairment Questionnaire (WPAI-OA) [27] at 6- and 12-months post-randomisation.
- Health-related quality of life will be measured using the EQ-5D-5L at 6- and 12-months post-randomisation. The EQ-5D-5L [28] is a validated measure of health-related quality of life in terms of 5 dimensions (mobility, ability to self-care, ability to undertake usual activities, pain and discomfort, anxiety and depression) each with 5 levels of severity.
- Healthcare resource use at 6- and 12-months will be measured via a custom questionnaire, based on the Client Services Receipt Inventory. Included within this questionnaire will be additional physiotherapy (above that provided to the CMT arm), GP appointments, corticosteroid injections, surgery, imaging, hospital stays and medication use.
- All-cause mortality.
- Adverse events attributable to the trial.
- Serious adverse events.

Our choice of outcomes includes instruments to capture pain, stiffness, activity limitation, psychological factors, global assessment of knee symptoms, quality of life, healthcare resource utilisation and adverse events, including mortality. This outcome set is sufficiently broad to include all components of a core outcome set recommended by OMERACT-OARSI (Outcome Measures in Rheumatology-Osteoarthritis Research Society International) for clinical trials in knee osteoarthritis [24].

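### Section 3.1 promises treatment-effect estimates for GAKS and knee replacement, but Section 10.5 makes GAKS descriptive only and leaves knee replacement off the analysed list, although Section 10.9 relies on that contrast

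*Protocol*

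**What the plan says.** Protocol Section 3.1 gives as a secondary aim "Estimates of treatment effects across a range of secondary outcomes including knee pain, knee function" and continues the list with "global assessment of knee symptoms, quality of life, the impact of knee OA on capacity to work" and "healthcare use (including knee replacement surgery) and adverse events up to 12-months". Section 3.3 then lists as secondary outcomes "Global assessment of knee symptoms (GAKS) at 6- and 12-months post-randomisation" and, separately, "Healthcare resource use at 6- and 12-months will be measured via a custom questionnaire". Surgery is one item of that questionnaire, and knee replacement is not listed as an outcome in its own right.

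Section 10.5 opens with a general rule that secondary outcomes follow the methodology of the primary analysis. It then lists what will be analysed: composite WOMAC at 6 months, and the WOMAC subscales, PCS, PSEQ, WPAI-OA and EQ-5D-5L at 6 and 12 months. GAKS has its own sentence after the list: "Descriptive statistics will be provided for the Global assessment of knee symptoms (GAKS) at 6 and 12 months". The stated purpose of that description is to understand differences between the arms. Healthcare use, knee replacement and adverse events do not appear.

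Two later steps rest on knee replacement. Section 8.7 begins one of them with "If the final data indicates any difference in the rate of knee replacement between the CMT and control arm" and goes on to say that funding for a 10-year follow-up will be sought. Section 10.9 runs a lifetime-horizon economic model if the arms differ significantly in EQ-5D-5L or in the knee-replacement rate.

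**The concern.** For GAKS the protocol commits itself to two incompatible things: an estimated treatment effect in the aim, and description only in the analysis section. A later analysis plan that follows Section 10.5 faithfully would carry the mismatch forward. The report would show GAKS summaries by arm with no effect estimate or confidence interval, so readers could not tell a chance difference from a real one. The telephone minimum dataset in Section 8.8 keeps only WOMAC, GAKS and EQ-5D-5L. GAKS is therefore one of the outcomes the trial works hardest to complete, and the only one of those three that is not to be estimated.

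For knee replacement the issue is a missing link. A decision in Section 10.9 turns on whether the rates differ significantly, and no section defines the estimate or the test. The two triggers also set different thresholds, any difference in Section 8.7 and a significant one in Section 10.9, although Section 8.7 refers the reader to the economic section.

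**Working it through.** **Aim against analysis plan**

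| Named in the Section 3.1 aim | Treatment in Section 10.5 |
|---|---|
| Knee pain, function, stiffness | Analysed (WOMAC subscales) |
| Pain catastrophizing, self-efficacy | Analysed (PCS, PSEQ) |
| Quality of life, capacity to work | Analysed (EQ-5D-5L, WPAI-OA) |
| Global assessment of knee symptoms | Descriptive only |
| Healthcare use, including knee replacement | Not listed; healthcare use feeds the costs in 10.9 |
| Adverse events | Not listed |

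Seven of the ten named items are covered, one is described only, and two are absent.

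**Does the general rule in 10.5 fill the gap?** The primary model in Section 10.4 is a linear multilevel ANCOVA with baseline WOMAC as covariate and site and receipt of surgery as random effects. For GAKS, the specific sentence overrides the general rule. For knee replacement, a linear model that itself contains receipt of surgery cannot be carried over unchanged to a yes/no surgical outcome.

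**Planned sample size (Section 10.1).** Effect size 0.46, two-sided 5%, 90% power: a two-sample t-test calculation gives 100.28, hence 101 per group, as stated. Allowing for 20% attrition, 101/0.8 = 126.25, stated as 126. The figure reproduces and is not in dispute; 101 per arm is used below.

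**Precision for knee replacement (illustration).** The protocol gives no rate, so control rates of 5% to 20% and a halving in the CMT arm are assumed.

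Half-width = 1.96 × √[(p1(1−p1) + p2(1−p2))/101]

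- 5% vs 2.5%: 1.96 × √(0.071875/101) = 5.2 points
- 10% vs 5%: 1.96 × √(0.1375/101) = 7.2 points
- 15% vs 7.5%: 1.96 × √(0.196875/101) = 8.7 points
- 20% vs 10%: 1.96 × √(0.25/101) = 9.8 points

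Power to detect these halvings is about 15%, 27%, 39% and 51%. In the first three cases the half-width exceeds the difference itself. Healthcare use is not in the telephone minimum dataset, so fewer than 101 per arm may have this outcome, and these figures may be optimistic.

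**Precision for GAKS (illustration).** The response format is not in the protocol. If GAKS were reduced to a proportion improved, half-width = 1.96 × √(2p(1−p)/101):

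- p = 0.3: 1.96 × √(0.42/101) = 12.6 points
- p = 0.5: 1.96 × √(0.50/101) = 13.8 points

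On that assumption, two arms could differ by 10 points by chance with nothing in a purely descriptive table to show it.

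**The case against.** Much of the case on the other side is sound and limits the point.

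- **GAKS and knee replacement are different cases.** Only GAKS has a stated method that conflicts with the aim. Knee replacement and healthcare use are absent from a list, and how to model a binary or resource-use outcome is commonly left to an analysis plan. This stands. What keeps knee replacement in the point is that the protocol hangs a decision on the contrast.
- **A reader might infer that no comparison of knee replacement is intended.** The documents do not support that. Sections 8.7 and 10.9 both presuppose one; what they lack is its definition.
- **A reader might infer that the 10-year follow-up itself depends on an undefined contrast.** Both sections speak only of seeking or applying for funding. The lifetime model is the step triggered directly, and EQ-5D-5L is an alternative route to it.
- **A reader might infer that GAKS cannot be modelled because it has no baseline value.** It is recalled change, collected only at 6 and 12 months. The covariate in the primary model is baseline WOMAC, which is collected, so adjustment remains possible.
- **Describing a recalled-change item in an unblinded trial is a defensible choice.** It may be, but Section 3.1 would then have to say so. The GAKS sentence also states a purpose, understanding between-arm differences, that description alone serves poorly.
- **The numbers rest on assumed rates and an assumed format.** They do. They show precision, not harm, and they show that the knee-replacement contrast would be weak.

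**Conclusion.** The point holds in limited form. Sections 3.1 and 10.5 contradict each other on GAKS, and the plan as written yields no effect estimate or confidence interval for an outcome named in the aim. Knee replacement is promised in the same aim, omitted from the analysed list, and then used in Section 10.9 as a trigger with no defined estimate.

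It would go too far to say that Section 10.5 fails the secondary aim as a whole. It covers pain, function, stiffness, catastrophizing, self-efficacy, quality of life and work. Of the rest, healthcare use enters the costs in Section 10.9, which gives cost-effectiveness rather than a treatment effect on use, and adverse events are not addressed in Section 10.5. The primary conclusion is unaffected.

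The contradiction needs no assumption. The sizes do: about 7 points for the knee-replacement half-width at 10% against 5%, with 5.2 to 9.8 points across the assumed range, and 12.6 to 13.8 points for GAKS if it is dichotomised. This should be corrected before outcome data are seen, so that the choice of method cannot be influenced by the results.

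**What to change.** 1. In Section 10.5, replace the GAKS sentence with a between-arm comparison at 6 and 12 months, adjusted for baseline composite WOMAC and site. Report an effect estimate with 95% CI beside the descriptive summary. Match the model to the response format: ordinal logistic regression for an ordered categorical scale, linear for a numeric one.
2. Add knee replacement by 12 months to the analysed list as a risk difference with 95% CI. The outcome should be knee replacement specifically, since Sections 8.7 and 10.9 refer to that and not to knee surgery in general.
3. Use that one estimate for both later decisions, and reconcile the thresholds in Sections 8.7 and 10.9.

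If the team prefers to keep GAKS descriptive, the minimum is to reword Section 3.1 so that it no longer promises an effect estimate for it.

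The cost is a short amendment and two more secondary estimates on data already planned for collection. The knee-replacement interval will be wide and should be presented as such. On the assumed rates, a significance threshold would often be missed even if the rate were halved.
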